### 11. DESCRIPTIVE STATISTICS

## 11.1 Subject Disposition

A descriptive summary of subject disposition will be provided to summarize the number of subjects screened, randomized, treated and eligible for the ITT or Safety Analysis Set populations. Additionally, the number of subjects who have completed or discontinued treatment at the 6-month time point will be summarized, along with their reasons for discontinuation. In particular, those subjects who discontinue treatment or study follow up due to adverse events will be reported.

## 11.2 Demographic and Baseline Characteristics

The demographic and baseline characteristics listed in section 9.2 will be summarized for the ITT population according to the general considerations described in Section 9. The baseline characteristics of each treatment group will be observed and compared descriptively, with summary statistics provided per treatment group.

## 12. ANALYSIS CORRESPONDING TO THE STUDY OBJECTIVES

### 12.1 Efficacy

The clinical performance of the VeSTAL device, in comparison to the sham control device will be evaluated using efficacy analyses performed on the ITT analysis population and categorised as

Neurovalens Limited Identifier: EXP18020

Clinical Study Identifier: 243973

primary, supportive and secondary efficacy. The primary efficacy analysis results, in combination with the supportive efficacy analysis results will be utilized to consider the success of the study.

## 12.1.1 Primary Efficacy Analyses

As the primary efficacy endpoints differ between regulatory clearance pathways, the primary efficacy analyses also differ accordingly.

For both the *EU and USA regulatory clearance pathways*, the primary efficacy endpoint will be summarized using summary statistics for the percentage weight loss at the 6 month time point. The mean percentage weight loss will also be presented graphically, by treatment group, over time. Summaries and graphical outputs will be produced for observed data unless specified otherwise..

For the continuous efficacy endpoint, mean percentage weight loss at 6 months, the difference between treatment groups will be assessed using a linear model controlling for covariates of interest: gender and baseline weight. The least square (LS) mean difference between groups will be assessed for a statistically significantly difference from 0 i.e. p-value <0.05. For the USA regulatory clearance pathway, the lower limit of the confidence interval of the LS Mean difference between groups will be assessed against the 2% target for a successful study, whereas the EU regulatory clearance pathway will assess whether the LS mean difference between groups is significantly different from zero. Analysis using multiple imputation for missing data will be primary, with the LOCF and BOCF imputation methods used for supportive analyses.

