### 24. Treatment Procedure

### 24.1 Randomization / Assignment of subjects to treatment groups

Treatment assignments, investigation or sham devices will be generated via a randomized procedure, with participants randomly chosen in permuted blocks. At baseline, subjects will be assigned 1:1 between treatment (investigational device) and control groups (sham device). Stratification will be performed by gender and center.

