### Methods: Primary Aims

For total body weight loss (TBWL) as a continuous measure, we will use a linear regression with TBWL at each time period as the dependent variable and group and other covariates of interest (baseline total body weight, gender, age, study site) as independent variables. As a supportive analysis, we will also a two-sample t-test to examine the differences between the control and active treatment groups at each time period. To assess any longitudinal effects, we will use a linear mixed effects model for weight over time, with fixed covariates for baseline weight, time, group, and a time / group interaction, and a random intercept to account for within-subject correlation. We will use these models to generate two-sided 95% confidence intervals for the difference in mean percent weight loss.

We will calculate exact binomial confidence intervals (95%, two-sided) to determine if the response rate in the treatment group significantly exceeds 50%, with response defined by a loss of at least 5% of their body weight at the 6-month follow-up. As supportive analyses we will also use Fisher's exact test to compare the response rates in each group, and, will consider the use of a logistic regression to control for any other covariates of interest. To investigate possible longitudinal trends, we will fit a logistic mixed effects model, similar to the linear mixed effects model described above.

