### Missing Data

The primary hypotheses will be tested on the intent-to-treat population. Missing data will be clearly reported and included in tables. We will assess the assumption that the data is missing completely at random. For the primary effectiveness analysis of total body weight loss (TBWL) as a continuous measure we will perform a multiple imputation analysis. We will include the same covariates in the multiple imputation model as in the linear regression, i.e. group, baseline total body weight, gender, age, study site. Two supportive sensitivity analyses with different approaches to imputing missing data will also be performed: last observation carried forward (LOCF) and baseline value carried forward (ie assuming no weight loss).

A sensitivity analysis will be performed with the binary weight loss endpoint. This analysis will include a bestcase scenario (assuming subjects with missing values have all lost over 5% body weight), a worst-case scenario (assuming no subjects with missing values have lost over 5% body weight), and a tipping point analysis (as described in Yan et al., 2009).

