#### 9.2 Independent Variables

Independent variables will be comprised of demographic randomisation stratification factors and baseline values for the relevant endpoint and will be utilised as covariates when investigating differences between treatment groups for the dependent primary efficacy endpoints.

Such endpoints will include:

- Gender (stratification factor)
- Baseline value, e.g. weight (kg), body fat (kg)

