### 10.2 Premature Withdrawal and Missing Data

All subjects enrolled into the study who meet the requirements for the ITT or Safety Analysis Set population will be included in the final analyses. This will include those subjects who withdrew from the study prematurely or have missing data.

For the large part, subjects will contribute what data they have available without imputation. However, for the primary efficacy endpoint of total body weight loss, three approaches to missing or incomplete data will be taken, under the assumption that the data is missing at random:

- 1. Multiple imputation will be applied by means of a multiple imputation model which is composed of three steps:
  - 1.1. The missing data are imputed multiple times to generate multiple sets of data. The imputed values are predicted total body weight loss values obtained from a linear regression model with observed total body weight loss data as the dependent endpoint, and the same covariates of interest that are used to adjust the primary endpoint (treatment group, gender and baseline weight). By providing 75 imputations per missing value, the variability between imputed values represents the uncertainty over the missing value.
  - 1.2. The 75 complete datasets are analyzed using the planned statistical analysis as per section 12.1.1. The results from the 75 complete datasets are then combined to produce an estimate for the primary endpoint, which reflects the uncertainty due to the missing values.
- 2. Last Observation Carried Forward (LOCF) will be applied for all subjects without data, inclusive of those who have withdrawn from the trial and subjects who have not reached the time point.
- 3. Baseline Observation Carried Forward (BOCF) will be applied for all subjects without data, inclusive of those who have withdrawn from the trial and subjects who have not reached the time point.

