## 12.1.3 Secondary Efficacy Analyses

For both the *EU and USA regulatory clearance pathways*, secondary efficacy analyses will be performed to investigate the difference between treatment groups (using multiple imputation, LOCF and BOCF for missing data for weight outcomes, observed data for other outcomes) in:

- Mean percentage weight loss;
  - A t-test will be used to detect a statistically significant difference (p-value < 0.05)

     between the mean percentage weight loss per group (unadjusted analysis).
  - The mean percentage weight loss between groups, having accounted for covariates of interest and repeated measures over time. In order to do so, a mixed effect repeated measures (MMRM) model will be developed using percentage weight loss at 3 and 6 months) and controlling for the prespecified covariates of interest: gender and baseline weight. Subject will be included in the mixed effects model as a random effect with an unstructured covariance structure. If a convergent model cannot be achieved with an unstructured covariance, further covariance structures will be tested sequentially until a satisfactory model has been achieved.
  - Plot of the Ismeans of change from baseline at 3 and 6 months obtained from the MMRM analysis described above with MI for missing data only
- Adjusted response rate;
  - o whereby response is defined as a subject achieving a percentage weight loss of at least 5% by 6 months. The adjusted response rate will be obtained by means of a logistic regression model with a binary response indicator as the dependent variable, treatment group as the explanatory variable and adjusting for covariates of interest: gender and baseline weight.
- Mean percentage VAT loss;
  - Summary statistics for percentage VAT loss at 3 and 6 months from baseline by treatment group
  - o Plotted graphically by treatment group over time
  - A linear model will be used for the mean percentage VAT loss at 6 months having adjusted for covariates of interest: gender and baseline VAT. The least square (LS) mean difference between groups will be assessed for a statistically significantly difference from 0 i.e. p-value <0.05.

- Mean percentage fat loss;
  - Summary statistics for percentage fat loss at 3 and 6 months from baseline by treatment group
  - Plotted graphically by treatment group over time

Neurovalens Limited Identifier: EXP18020

Clinical Study Identifier: 243973

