### Blood endpoints;

- For the following endpoints, a statistical comparison will be performed between treatment groups at 6 months, using a linear model, with the endpoint as the dependent variable and treatment group, gender and baseline value as the explanatory variables. Data will be summarised descriptively and plotted graphically over time:
  - Percentage change in LDL
  - Change in atherogenic index
  - Change in high-sensitivity C-reactive protein
- Quality of Life endpoint: A statistical comparison will be performed between treatment groups for the change from baseline in the total IWQOL score at 6 months, using a linear model, with the change from baseline in total IWQOL score as the dependent variable and treatment group, gender and baseline score as the explanatory variables. Data will be summarised descriptively over time:
- Modifiable activity questionnaire;
  - Questionnaire responses from the modifiable activity questionnaire will be summarized per treatment group at 0 and 6 months for the following endpoints:
    - Total Physical Activity averaged over the past year in hours per week
    - Total Physical Activity averaged over the past year in MET-hours per week
- Concomitant medication adjustments
  - The changes in cardiovascular and/or initiation of diabetic medications will be summarized in terms of an increase, decrease or no change in concomitant medication, by treatment group. This assessment will be made by suitably qualified members of the study team. (It is not anticipated that any subjects will start the study on anti-diabetic medications as having diabetes mellitus is an exclusion criterion to

Neurovalens Limited Identifier: EXP18020

Clinical Study Identifier: 243973

enrolment, but it is possible that some may develop the condition during the course of the study).

Concomitant medications will also be summarized by treatment group according to
potential impact on weight status. These will be classified as medications that could
potentially cause either weight gain or weight loss as deemed by the Chief
Investigator.

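### Center is a randomisation stratum and a covariate in the protocol's primary model, but the SAP drops it from the primary and imputation models without giving a reason

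*SAP*

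**What the plan says.** **Randomisation.** Protocol 24.1, repeated in 34.1: "Stratification will be performed by gender and center". Allocation is 1:1 in permuted blocks.

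**Protocol model.** Section 34.1 (Methods: Primary Aims) regresses weight loss on group and "other covariates of interest (baseline total body weight, gender, age, study site) as independent variables". Its Missing Data paragraph uses the same list for multiple imputation: "i.e. group, baseline total body weight, gender, age, study site". The synopsis is looser and names only gender and age as examples.

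**SAP model.** In 12.1.1 the group difference in percentage weight loss at 6 months "will be assessed using a linear model controlling for covariates of interest: gender and baseline weight". The imputation model in 10.2 takes the "covariates of interest that are used to adjust the primary endpoint (treatment group, gender and baseline weight"). The repeated-measures model in 12.1.3 is fitted "controlling for the prespecified covariates of interest: gender and baseline weight". The blood endpoints use "treatment group, gender and baseline value as the explanatory variables", and the other label-claim models are built alike.

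**The SAP's covariate rule.** Section 9.2: "Independent variables will be comprised of demographic randomisation stratification factors and baseline values for the relevant endpoint". It then lists gender, marked as a stratification factor, and the baseline value. Center is not listed. Section 13, item 7, also justifies gender as the stratification factor.

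**Geography elsewhere in the SAP.** Section 9.3 adds a two-level region (US, non-US) and its interaction with treatment for the poolability and subgroup analyses only.

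**The concern.** Blocking within center balances the arms on whatever differs between centers. That reduces the true sampling variance of the treatment difference. A model without center does not credit the reduction: between-center variation stays in the residual, and the reported standard error exceeds the true one. The confidence interval is then too wide. The US mean criterion requires the lower confidence limit to clear 2%, and power for that is only about 80%.

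The documents make a center effect plausible without quantifying it. Dietician time at the last visit is one hour at the US sites and about 30 minutes in Northern Ireland. The Texas site also recruits from its own patient database. The DXA scanners differ between the US and Northern Ireland, which bears on the fat, visceral fat and lean-mass claims.

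Two further points follow. The protocol and the SAP specify different covariates for the same primary test. And if dropout and weight loss both vary by center, an imputation model without center makes the missing-at-random assumption in SAP 10.2 harder to defend.

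**Working it through.** **Inputs from the documents.** True difference 6.6 − 3.1 = 3.5 points; margin 2, so the distance to the margin is 1.5; SD 3.9; correlation of baseline weight with weight loss 0.4 in absolute value (the protocol prints −0.4 and the SAP 0.4; the sign does not affect residual variance); 90 per arm; 2.5% one-sided.

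**Assumptions.** The share f of residual variance due to center is not given; I use 0, 2, 5 and 10%. The simulation also assumes blocks of 4 and 70% women.

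**The plan's own figure.** The plan claims more than 80% power for both US criteria together at N = 180.
- Residual SD = 3.9 × √(1 − 0.4²) = 3.574.
- SE = 3.574 × √(2/90) = 0.533.
- Power of the mean criterion = Φ(1.5/0.533 − 1.96) = 80.4%.
- The responder criterion alone (at least 55 of 90, response probability Φ(1.6/3.9) = 0.659) has 85.8%.
- Simulated joint power is about 73%, so the claim for both criteria is not reproduced under the 2.5% one-sided rules. That is a separate matter. The mean-criterion figure is the base for what follows.

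**Effect of omitting center.** With arms balanced within center, the true SE is 0.533 × √(1 − f), while the model without center still reports 0.533.
- One-sided size without center = 1 − Φ(1.96/√(1 − f))
- Power without center = Φ((1.5 − 1.96 × 0.533)/(0.533 × √(1 − f)))
- Power with center = Φ(1.5/(0.533 × √(1 − f)) − 1.96)

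For f = 10%, √0.9 = 0.949 and the true SE is 0.5055. Size is 1 − Φ(2.066) = 1.94%. Power is Φ(0.901) = 81.6% without center and Φ(1.007) = 84.3% with it.

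| f | SE overstated by 1/√(1 − f) − 1 | Size without center | Power without → with |
|---|---|---|---|
| 0% | 0% | 2.50% | 80.4 → 80.4% |
| 2% | 1.0% | 2.39% | 80.6 → 81.2% |
| 5% | 2.6% | 2.22% | 81.0 → 82.3% |
| 10% | 5.4% | 1.94% | 81.6 → 84.3% |

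**Simulation check.** 100,000 runs per setting; centers of 64, 36, 56 and 24 (180 split in the protocol's ratio 106:60:94:40); blocks within center × gender; t tests on 176 df without center and 173 with.

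| f | Power without → with | Gain (points) | Size without → with |
|---|---|---|---|
| 0% | 79.70 → 79.69% | 0.0 | 2.43 → 2.44% |
| 2% | 79.94 → 80.47% | 0.5 | 2.33 → 2.44% |
| 5% | 80.25 → 81.67% | 1.4 | 2.17 → 2.44% |
| 10% | 80.84 → 83.64% | 2.8 | 1.90 → 2.44% |

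Under the SAP's site ratio (106:100:94:40) the gains are −0.1, 0.5, 1.4 and 2.8 points.

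**The case against.** **The consequence is small and conditional.** This stands. There is no bias and no inflation of type I error, and power under the SAP model never falls below its no-center value. The loss exists only relative to a center-adjusted analysis and only if center matters.

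**US success needs both criteria.** This also stands. The responder criterion is a one-arm exact interval that center reaches only through imputed weights. The gain in joint success is therefore smaller: about 0, 0.5, 1.1 and 1.9 points over the same range (20,000 runs). The EU test is against zero, where power is essentially 100% either way.

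**The simulation is not the planned analysis.** True: it uses 180 complete cases, not multiple imputation on all randomised subjects. The effect of omitting center from the imputation model has not been quantified.

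**SAP 9.2 limits covariates to demographic stratification factors.** That wording may explain how center fell out, but it gives no statistical reason. The argument in section 13, item 3, that adjusting for baseline attributes gives a more powerful test, favours center too.

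**Most secondary models are not departures.** Correct. The protocol's longitudinal model has no site term, and its default secondary test is an unadjusted t-test. Adding center there is for consistency, not to restore the protocol.

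**The SAP supersedes the protocol, and version 1.1 was agreed with FDA.** The documents do not show whether the covariate list was discussed. Section 13 measures itself against protocol Version 5, which is not available, so it cannot be called incomplete against that version. It can be said that the SAP differs from Revision 11 on site and age without explanation.

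**Region is examined.** It is, but only in subgroup and follow-up models. It does not enter the primary test or separate the three US centers.

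**Conclusion.** The concern holds. The SAP omits a stratification factor that the current protocol includes in the same model, and gives no reason. The primary test stays valid and errs on the conservative side. For center shares of 2 to 10% of residual variance, which are assumed, the cost is about 0.5 to 2.8 points of power on the US mean criterion, and about 0.5 to 1.9 points on joint US success. It is nil if center has no effect, and nil for the EU pathway. These figures rest on the plan's own means, SD and correlation, on 180 complete cases, and on the assumed block size and gender mix. The change should be made because it is cheap and removes a discrepancy in the primary model; the trial does not fail without it.

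**What to change.** Before unblinding:

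1. Add center (CCR, EPARC, UU, TDE) as a fixed effect in the primary linear model and the imputation model. For consistency, do the same in the repeated-measures and label-claim models.
2. Fix a pooling rule now. For example, borrow the SAP's subgroup threshold: if EPARC or TDE has fewer than 10 randomised subjects in either arm, merge it with CCR. Keep UU separate as the only non-US site.
3. List center in SAP 9.2 as a stratification factor.
4. Refer section 13 to protocol Revision 11, and state and justify any protocol covariate left out, such as age.

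The cost is 3 degrees of freedom and a short edit; center is already recorded. Pooling may not be needed. In proportion to the site figures, TDE would supply 40/300 × 200 ≈ 27 subjects (protocol) or 40/340 × 200 ≈ 24 (SAP), about 12 to 13 per arm. The protocol gives its site figures as upper limits and expects TDE to open about a year after the first sites, so TDE could fall below 10 per arm; the rule should therefore be written down in advance.

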## Study Acceptance Criterion EU:

• Mean: There should be at least a 2% total body weight loss (TBWL) superiority margin between the active-product and sham-treated groups.

This weight loss efficacy acceptance criterion must be met to claim success. This criterion can be specified in mathematical formulae as follows:

```
mA - mC \ge 2\% and pt \le 0.05
```

Where:

mA and mC are the observed mean percentage weight loss on active and control respectively pt is the p-value (two-sided) from a linear regression comparing percentage weight loss between active and control (H0:  $\mu$ A =  $\mu$ C; H1:  $\mu$ A  $\neq \mu$ C)

 $\mu A$  and  $\mu C$  are the underlying population mean percentage weight loss on active and control respectively

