### Primary Outcome Measure EU (At 6 months)

1. Mean: There should be at least a 2% total body weight loss (TBWL) superiority margin between the active-product and sham-treated groups.

This criterion can be specified in formulae as follows:

 $mA - mC \ge 2\%$  and  $pt \le 0.05$ 

Where:

mA and mC are the observed mean percentage weight loss on active and control respectively pt is the p-value (two-sided) from a linear regression comparing percentage weight loss between active and control (H0:  $\mu$ A =  $\mu$ C; H1:  $\mu$ A  $\neq \mu$ C)

 $\mu A$  and  $\mu C$  are the underlying population mean percentage weight loss on active and control respectively

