# Neurovalens Limited Identifier: EXP18020

Clinical Study Identifier: 243973

For the purpose of the *EU regulatory clearance pathway*, the study will be deemed to have met the efficacy criteria if the hypothesis is rejected, and the following numerical criterion is achieved:

• The difference between the mean percentage weight loss of participants using the VeSTAL device and the sham control is at least 2% as observed from the mean estimates.

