### 9.4 Multiple Comparisons and Multiplicity

The primary efficacy endpoint, percentage total body weight loss from baseline will be assessed at the 6-month timepoint and therefore will not require any adjustment for multiplicity or multiple comparisons. As a result, to control the type I error rate, the threshold of significance will be set at the 5% alpha level, such that statistical significance will require p<0.05 (two-sided).

As the secondary endpoints analyzed with the intention of making a labelling claim will be assessed sequentially, with a predefined ordering, there will be no adjustments made to the alpha level for multiple testing.

If a significant difference is achieved for the primary endpoint at 6 months, the study will continue to assess the secondary endpoints in the following order: VAT loss, LDL, fat loss, lean muscle mass, atherogenic index, systemic inflammation, calorie intake and quality of life. Each endpoint can only be assessed if the criterion for the previous endpoints have been met and all endpoints will be assessed using a nominal alpha level of significance set at 5%.

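### SAP 12.1.1 describes the EU pathway only as a test against zero, while SAP 2.3.1 and the protocol also require an observed difference of at least 2%; 12.1.1 should carry the full two-part rule.

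*SAP*

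**What the plan says.** **Protocol.** The synopsis, 18.2 and 34.3 give the same EU rule. In words: "There should be at least a 2% total body weight loss (TBWL) superiority margin between the active-product and sham-treated groups". In symbols: mA − mC ≥ 2% together with a p-value of at most 0.05. Section 18.2 defines the terms: "mA and mC are the observed mean percentage weight loss on active and control respectively". Section 34.3 adds that "pt is the p-value (two-sided) from a linear regression comparing percentage weight loss between active and control".

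**SAP 2.3.1.** The EU pathway meets the "efficacy criteria if the hypothesis is rejected, and the following numerical criterion is achieved", and that criterion is that the difference between VeSTAL and "the sham control is at least 2% as observed from the mean estimates".

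**SAP 12.1.1.** The primary model for percentage weight loss at 6 months is linear, with gender and baseline weight as covariates and multiple imputation for missing data. For the USA, the lower confidence limit of the LS mean difference is compared with the 2% target. The sentence then continues: "whereas the EU regulatory clearance pathway will assess whether the LS mean difference between groups is significantly different from zero". No 2% condition is given for the EU.

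**Neighbouring SAP sections.** Section 12.1 says that primary and supportive results together inform study success, and 12.1.2 says that the EU pathway needs no supportive analyses. Section 9.4 opens the labelling-claim sequence on a significant primary difference and does not name 2%. Section 13 lists changes from the protocol, and removal of the EU threshold is not among them.

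**The concern.** Someone programming or reporting the primary analysis would work from section 12. There the two pathways are set against each other in one sentence: a 2% target for the USA, a test against zero for the EU. Because 12.1.2 adds nothing for the EU, a reader who stays within section 12 finds significance as the only EU condition. A reader who goes to 2.3.1 or the protocol finds a second condition.

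This is a decision threshold for a regulatory claim. If the observed difference were significant but below 2 points, two sections of one plan could be cited for opposite conclusions, and the choice between them would be made after the result was known. The 12.1.1 wording also gives no direction for the EU test; the 2% condition is what supplies one. Finally, no document says which estimate is to be compared with 2%, which matters if the result falls close to that line.

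**Working it through.** **The plan's own figures.** The plan states no power for the EU rule. The recruitment arithmetic reproduces: 180 / (1 − 0.10) = 200. The stated power of more than 80% refers to the two USA criteria jointly. In simulation it comes out at about 86% if the mean criterion is read as an observed difference of at least 2% with p < 0.05, and about 69–72% if the lower confidence limit must exceed 2%. That is a separate matter and does not bear on this point.

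**Inputs** (SAP 5, SAP 9.4, SAP 12.1.1)
- SD of percentage weight loss: 3.9 in each arm
- Evaluable subjects: 180, allocated 1:1, so 90 per arm
- Correlation of baseline weight with weight loss: 0.4 in size (the SAP prints 0.4 and the protocol −0.4; the sign does not affect the residual SD)
- Two-sided 5% level
- Design difference: 6.6 − 3.1 = 3.5 points

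**Smallest significant observed difference**
- Unadjusted: SE = 3.9 × √(2/90) = 0.581. With the t quantile the cut-off is 1.147, about 1.15 points (1.139 with the normal quantile).
- Adjusted for baseline weight: residual SD = 3.9 × √(1 − 0.4²) = 3.574 and SE = 3.574 × √(2/90) = 0.533. The cut-off is 1.052, about 1.05 points (1.044 with the normal quantile).
- With 100 per arm complete, the t cut-offs are 1.088 unadjusted and 0.997 adjusted.

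At 90 per arm, an observed result between about 1.05 (adjusted) or 1.15 (unadjusted) and 2.0 points would therefore pass a significance-only rule and fail the two-part rule.

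**Chance of passing at 90 per arm.** For significance in favour of active: 1 − Φ((c − δ)/SE), where c is the normal-quantile cut-off and δ the true difference. For the two-part rule, c is replaced by 2.0, the larger of the two thresholds.

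| True difference | Significance only, unadjusted / adjusted | Significance and ≥ 2%, unadjusted / adjusted |
|---|---|---|
| 0 | 2.5% / 2.5% | 0.03% / 0.01% |
| 1.1 | 47% / 54% | 6.1% / 4.6% |
| 1.5 | 73% / 80% | 19% / 17% |
| 2.0 | 93% / 96% | 50% / 50% |
| 3.5 (design) | >99.9% / >99.9% | 99.5% / 99.8% |

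For example, at δ = 1.5 unadjusted: (1.139 − 1.5)/0.581 = −0.62, giving 73%; (2.0 − 1.5)/0.581 = 0.86, giving 19%. A simulation of the baseline-adjusted model at δ = 1.5 gave 79% and 18%, in line with the formula.

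**The case against.** The strongest reply is that nothing has been removed. SAP 2.3.1 is the only SAP text that says when the EU pathway is deemed to have met its efficacy criteria, and it keeps both parts. There the pathways differ in where the 2% is read, from the confidence interval for the USA and from the mean estimates for the EU, and not in whether it applies. Section 12.1.1 can be taken as describing which test is run. It never says that significance alone suffices for the EU, and its reference to a successful study sits in the USA clause. The documents do not rank 12.1.1 above 2.3.1.

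That reply stands against two stronger inferences:
- A reader might infer that the SAP dropped the EU threshold. The documents do not support this: 2.3.1 retains it, and section 13 records no such change.
- A reader might infer that the protocol prescribes raw means and the SAP prescribes LS means. Neither is stated. In the protocol, the observed means are contrasted with underlying population means, which separates estimates from parameters. SAP 2.3.1 speaks only of mean estimates. The estimator is unspecified.

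The reply does not remove the gap. 12.1.1 sets out the two pathways side by side and gives the 2% for one only, no EU analysis follows in 12.1.2, and 9.4 does not name the 2% either. A later sentence in 9.4, about meeting the criterion for preceding endpoints, could be read as bringing it back, but that too is left to interpretation.

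It is also fair to say that true differences of 1.5 or 2.0 are scenarios chosen for illustration, and that at the design difference the choice of rule hardly matters.

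**Conclusion.** The point holds as an internal inconsistency: 12.1.1 is incomplete against an explicit two-part EU rule in SAP 2.3.1 and the protocol. It should be corrected, but it is not evidence that the EU criterion was relaxed.

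The size is conditional on 12.1.1 being read as the EU success rule. On that reading the disputed zone runs from about 1.05 (adjusted) or 1.15 (unadjusted) to 2.0 points at 90 per arm. The largest gaps in the table are at a true difference of 1.5 points: 73% against 19% unadjusted, 80% against 17% adjusted. At 3.5 points the rules differ by half a percentage point or less.

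A reader might go further and say that a 1.1-point result would count as success. That needs a qualification as well as the significance-only reading. With 180 evaluable subjects, an observed 1.1 gives p = 0.040 in the baseline-adjusted model but p = 0.060 unadjusted.

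The figures assume the planning SD of 3.9, a correlation of 0.4 where adjusted, approximate normality and 90 evaluable subjects per arm. They ignore gender adjustment and the added variance from multiple imputation, either of which could move the cut-offs slightly.

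**What to change.** In SAP 12.1.1, replace the EU clause with the same two-part rule as 2.3.1: EU success requires two-sided p < 0.05 in favour of active and a difference of at least 2 percentage points.

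Name one estimator for the 2% check and use it throughout. The LS mean difference from the primary multiple-imputation model is a natural candidate because it is also the quantity tested. The documents do not mandate it, so this is a choice for the sponsor to record.

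Then align the other places:
- SAP 2.3.1: name the estimator.
- SAP 9.4: say whether the labelling sequence for the EU opens on significance alone or on the full two-part criterion.
- Protocol synopsis, 18.2 and 34.3: use the same estimator in the definition of mA and mC.

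The cost is a few sentences across these sections, made before unblinding. No new data, analysis or change in sample size is needed.
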